### **9.2.2 Days 1-21**

The number of days each subject will actively engage with the study will vary according to the baseline measurements. Voltaren Gel use will be limited to 21 days, but study

Property of Haleon - Confidential

May not be used, divulged, published or otherwise disclosed without the consent of  
 Haleon

Clinical Protocol Template, TMF-187821, v11.0. Parent SOP: [CCI](#)

subjects are allowed to stop using the product if they do not feel the need to continue using it (e.g., if the pain subsides). Study subjects will be told to use the products as per label instructions. Actigraph will collect mobility and sleep-related information continuously (24/7) throughout the study.

All questionnaires will be provided at pre-specified time-points during the study ([please see schedule of activities table](#)). Safety, adverse events, and use of concomitant medications will be monitored throughout the study. If a subject stops using the product before Day 21 (post baseline), they will be prompted to complete all relevant questionnaires before concluding the study.

The following assessments will be completed by subjects during the study period:

- Subjects will report any changes in health, concomitant medications, or non-drug treatments/procedures.
- Subjects will use Actigraph and complete additional QoL questions each day.
- Subjects will complete an eDiary to record product use each day.
- Subjects will report any adverse events.
- Subjects will report the end of product use and answer end of the study questions prior to exiting the study.

Subjects who do not use the product at all throughout the study will be considered as dropouts. Partial usage of the product across the treatment period (Day 7 to Day 21) is allowed to capture RWE usage of the product.

### 9.2.3 End of Treatment Period/End Of Study

Subjects will have the option to discontinue treatment at their discretion. The reasons for discontinuing treatment will be captured whenever possible.

Subjects may choose to discontinue treatment if they feel that their symptoms do not warrant further use of the study product.

Subjects who wish to continue to use the study product will be prompted to discontinue treatment after the end of the study (28 days) and seek advice from their general practitioner for further assessment and treatment on their condition if needed.

Subjects will also be informed that the study will end on Day 21 (or the day after the last treatment, if earlier than 21 days), and will be asked to fill in an exit survey and perform final urine pregnancy test .

At the end of the study (Day 28), Actigraph device and the allocated product (used and unused) for this clinical study, should be returned to the Haleon Clinical Supplies Department or [CCI](#) using the return instructions provided.

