Planned Sample Size	
Sufficient individuals will be screened to enrol approximately 195 subjects assuming an estimated 25% drop out rate. It is believed that for this study 147 completed subjects are deemed sufficient to observe an improvement in QoL.
 
There were no previous similar studies measuring MVPA coupled with daily use of a diclofenac gel. Thus, the effect size was chosen based on literature review to detect even mild improvement in QoL factors: “An effect magnitude between 0.2 and 0.5 indicates mild improvement, between 0.5 and 0.8 indicates moderate improvement, and greater than 0.8 indicates considerable improvement in symptoms and QoL.” The sample size was based on a significance level (<math>\alpha</math>) = 0.05, Power (1-<math>\beta</math>) = 80%, and a standardized effect size of 0.25
 
Literature review also indicated that QoL scores are not normally distributed. Subjects with worse baseline symptoms showed larger improvement in QoL scores. Therefore, a two-sided non-parametric Wilcoxon Signed Rank test calculation was performed.
 
Using the above parameters, we obtain a sample size N =195 to retain the required 147 completed subjects. Therefore, it has been determined that 195 eligible subjects will be recruited for the trial, with an anticipated 147 study subjects expected to successfully complete the study.

Investigational Therapy	
Voltaren Gel 1% (diclofenac sodium) (US Only)
 
Voltaren Gel 1.16% (diclofenac diethylammonium) (EU Only)
 
Voltaren Gel 2.32% (diclofenac diethylammonium) (EU Only)

Treatment Duration/Intervention	
Actigraph device will be provided post patient consent at Day -7 to collect baseline information.
 
The baseline period will last between 3 (minimum) and 7 days (maximum), to collect enough information on both subjective and objective aspects of mobility and sleep quality.
 
End of baseline period will be considered day 0.
 
Post baseline period, (at Day 7 of the study) subjects will be provided with the product (Voltaren) and Actigraph device where there will be a total of 21 days of product usage and assessment of parameters as highlighted in the objectives.
 
Each subject will be in the study for 28 days maximum.

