**Table 1-1 Schedule of Activities**

Procedure/Assessment	Screening and Enrolment	Baseline *	Study Treatment Phase **						
	Day -7 (Visit 1)	D-7 to D0 (Visit 2)	D1	D1 to D6	D7	D8 to D13	D14	D15 to D20	D21 (Visit 3)
Informed Consent	X								
Inclusion/Exclusion Criteria	X								
Medical History	X								
Demographics	X								
Current/Prior concomitant medication review	X	X	X	X	X	X	X	X	X
Subject Eligibility	X								
Study Product use			X	X	X	X	X	X	X
Urine Pregnancy Test***	X								X
Dispensing of (Actigraph) a	X								
Dispensing of Product (Voltaren) a		X							
Pain									
Numeric Rating Scale b	X	X	X	X	X	X	X	X	X
Visual Analogue Scale b	X	X							
Western Ontario and McMaster University Osteoarthritis index (WOMAC) Pain Subscale b		X	X		X		X		X
Mobility									
Tracker-derived mobility assessment c		X	X	X	X	X	X	X	X
Western Ontario and McMaster University Osteoarthritis index (WOMAC) Stiffness Subscale b		X	X		X		X		X
Western Ontario and McMaster University Osteoarthritis index (WOMAC) Function Subscale b		X	X		X		X		X
Sleep									
Tracker-derived sleep assessment		X	X	X	X	X	X	X	X
Karolinska Sleepiness Scale b		X	X	X	X	X	X	X	X
Quality of Life									
EQ-5D-5L Quality of Life Questionnaire		X	X		X		X		X
Safety									
Adverse Events (AEs) Review c	X	X	X	X	X	X	X	X	X

Property of Haleon - Confidential

May not be used, divulged, published or otherwise disclosed without the consent of  
 Haleon

Clinical Protocol Template, TMF-187821, v11.0. Parent SOP: **CCI**

Procedure/Assessment	Screening and Enrolment	Baseline *	Study Treatment Phase **						
	Day -7 (Visit 1)	D-7 to D0 (Visit 2)	D1	D1 to D6	D7	D8 to D13	D14	D15 to D20	D21 (Visit 3)
Study Conclusion									
Returning Actigraph device and the allocated product									X
End of Study Questionnaires									X

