### **7.4      Investigational/Study Product Accountability**

All products supplied are for use only in this clinical study and should not be used for any other purpose.

All study products must be received by a designated person at the study sites, handled and stored safely and properly, and kept in a secured location to which only the staff have access. Upon receipt, all study products should be stored according to the instructions specified on the product labels. Study products are to be dispensed only to subjects enrolled in the study in accordance with the protocol, by authorized site staff.

The investigative site must maintain adequate records documenting the receipt, use, loss, or other disposition of all the product supplies. All study products will be accounted for

Property of Haleon - Confidential

May not be used, divulged, published or otherwise disclosed without the consent of  
Haleon

Clinical Protocol Template, TMF-187821, v11.0. Parent SOP: **CCI**

using the investigational/study product accountability form/record. The investigator is responsible for study product accountability, reconciliation, and record maintenance.

The accountability records must be available for inspection by the study monitor during the study. Monitoring of product accountability will be performed by the monitor during site visits and at the completion of the study.

At the end of the study (Day 28), Actigraph device and the allocated product (used and unused) for this clinical study, should be returned to the Haleon Clinical Supplies Department or **CCI** using the return instructions provided.

Detailed instructions for the return of study product for the accountability checks and subsequent destruction will be provided by Haleon or **CCI** during the study in time for study close out visit.

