## **11.9 Risks and benefits related to the participation in the clinical trial**

### **11.9.1 Risks related to Voltaren gel**

The Investigational Medicinal Product (IMP), Voltaren gel, is registered and marketed in countries concerned by the study. The IMP will be used in accordance with the indications, posology and safety product information approved.

Voltaren gel is contraindicated in the following circumstances:

- In patients with a known hypersensitivity to diclofenac or to any of the product excipients.
- In patients in whom asthma, angioedema, urticaria, or acute rhinitis are precipitated by acetylsalicylic acid or other non-steroidal anti-inflammatory drugs (NSAIDs).
- During the last trimester of pregnancy and during lactation/breastfeeding.

Special Warnings & Precautions for Use:

The possibility of experiencing systemic adverse events (those associated with the use of systemic forms of diclofenac) should be considered if Voltaren gel is used at a higher dosage or for a longer period of time than recommended.

Voltaren gel should be applied only to intact, non-diseased skin, and not to skin wounds or open injuries. It should not be allowed to come into contact with the eyes or mucous membranes and should not be ingested. Voltaren Emugel can be used with non-occlusive bandages but should not be used with an airtight occlusive dressing.

Interactions with other Medical Products and other Forms of Interaction:

Since systemic absorption of diclofenac from topical application is very low, interactions are unlikely.

Pregnancy & Lactation:

There are insufficient data on the use of diclofenac in pregnant women. Diclofenac should be used during the first two trimesters of pregnancy only if the expected benefit justifies the potential risk to the foetus. As with other NSAIDs, use of diclofenac during the third trimester of pregnancy is contraindicated owing to the possibility of uterine inertia, fetal renal impairment with subsequent oligohydramnios and/or premature closure of the ductus arteriosus.

Property of Haleon - Confidential

May not be used, divulged, published or otherwise disclosed without the consent of  
Haleon

Clinical Protocol Template, TMF-187821, v11.0. Parent SOP: **CCI**

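### Gel use is limited to 21 days, but the stop prompt and product return are also set at 28 days; with a baseline of 3 to 7 days the two agree only when baseline lasts 7.

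*Protocol*

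**What the plan says.** On the length of treatment, Protocol Section 9.2.2 says "Voltaren Gel use will be limited to 21 days". The synopsis (Treatment Duration/Intervention) agrees, describing a period "where there will be a total of 21 days of product usage". Table 1-1 schedules product use from Day 1 to Day 21 and places "Returning Actigraph device and the allocated product" in the Day 21 (Visit 3) column. Section 9.2.3 has subjects told that the study ends on Day 21, or the day after last treatment if that is earlier.

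Other passages use 28:

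- Section 9.2.3: subjects who wish to keep using the product "will be prompted to discontinue treatment after the end of the study (28 days").
- Section 7.4: "At the end of the study (Day 28), Actigraph device and the allocated product (used and unused") go back to the sponsor's supplies department or its contractor. Section 9.2.3 repeats this.
- Section 7.7: the rule for completing questionnaires on early stopping refers to stopping before Day 28. Section 9.2.2 gives the same rule for stopping before Day 21 post baseline.

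The start of treatment is also given in two ways. Section 9.2.1 makes the end of baseline Day 0, and Table 1-1 dispenses the gel at that visit. The synopsis says "Post baseline period, (at Day 7 of the study) subjects will be provided with the product (Voltaren"). Section 9.2.2 then describes the treatment period in these words: "Partial usage of the product across the treatment period (Day 7 to Day 21) is allowed to capture RWE usage of the product".

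Section 9.2.1 lets baseline last from 3 to 7 days and gives a maximum of 28 days in the study including baseline. SAP Section 7.1 counts study days from the baseline visit.

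**The concern.** A site reading these passages has two instructions on when a subject stops the gel and when the product comes back, and nothing that ranks one above the other. The two sets of day numbers appear to start at different points: one at screening, so that product is given at Day 7 and the study ends at Day 28, and one at the end of baseline, so that product is given at Day 0 and the study ends at Day 21. With a variable baseline they are not interchangeable.

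At stake is the maximum exposure and whether all of it falls within scheduled safety collection. Table 1-1 places the last adverse event review and the final pregnancy test at Day 21, and contact after the study is optional under Section 9.5. Any use between Day 21 and a later return would follow those assessments. It would also lengthen the SAP's duration of exposure, which runs to the last application date on the Study Termination page (SAP Sections 7.1 and 7.4.6). That duration is the denominator of treatment compliance, while the scheduled diary days that feed the numerator end at Day 21.

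**Working it through.** Inputs, all from the documents: limit on use, 21 days (Protocol synopsis and 9.2.2); baseline length b, 3 to 7 days (9.2.1); maximum time in study, 28 days including baseline (9.2.1); stop prompt at 28 days (9.2.3); product return at Day 28 (7.4, 9.2.3) and at Day 21 (Table 1-1).

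**The plan's own figure.** Longest baseline plus treatment: 7 + 21 = 28 days. The 28-day maximum is reproduced, but only for b = 7. In general a subject who finishes at treatment Day 21 has been in the study b + 21 days, which is 24, 25, 26, 27 or 28 days for b = 3 to 7.

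**Day 28 counted from screening.** If screening is day 0, Day 28 is treatment day 28 − b, and the excess over 21 is 28 − b − 21 = 7 − b. If screening is day 1, it is treatment day 27 − b, and the excess is 6 − b.

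| Baseline (days) | Treatment day, screening = day 0 | Days past 21 | Treatment day, screening = day 1 | Days past 21 |
|---|---|---|---|---|
| 3 | 25 | 4 | 24 | 3 |
| 4 | 24 | 3 | 23 | 2 |
| 5 | 23 | 2 | 22 | 1 |
| 6 | 22 | 1 | 21 | 0 |
| 7 | 21 | 0 | 20 | none |

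The largest excess is 4 days, or 4/21 = 19% of the stated limit; with screening as day 1 it is 3 days, or 3/21 = 14%.

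**Day 28 counted from the end of baseline.** The excess would be 28 − 21 = 7 days for every subject. Time in study would then be b + 28, that is 31 to 35 days, which exceeds the 28-day maximum including baseline.

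**The Day 7 to Day 21 label.** Counted from the end of baseline, it leaves out Days 1 to 6. Counted from screening with a 7-day baseline, it spans 21 − 7 = 14 days, not 21. It fits neither count.

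**Effect on the primary analysis.** SAP Section 7.4.7.1 uses study days up to 20, counted from the baseline visit, so later use of gel does not enter it.

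**The case against.** The strongest reply is that the 21-day limit is stated repeatedly and no passage says in terms that gel may be used for longer. The sentence on the stop prompt ties it to the end of the study, and its 28 days can be read as the whole-study maximum, 7 + 21. Dosing past Day 21 would also require the Visit 3 return to fail. Section 7.4 sits among the site accountability rules and could describe the site sending product to the sponsor, which need not conflict with subjects handing it in at Visit 3.

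Much of this stands. It makes extra dosing a possibility rather than an expected result. It does not remove the conflict. The shorthand reading is correct only for a 7-day baseline, and Sections 7.4, 7.7 and 9.2.3 do not say that they mean that case. The site-to-sponsor reading would explain Section 7.4, but not the stop prompt in Section 9.2.3 or the early-stopping rule in Section 7.7.

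Three stronger readings are tempting, and the documents do not support them:

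- A reader might infer a 7-day overrun (33%) for every subject. That conflicts with the 28-day maximum including baseline.
- A reader might link the extra days to the warning in Section 11.9.1 about systemic events if the gel is "used at a higher dosage or for a longer period of time than recommended". The recommended duration is on the product label, which the documents do not reproduce, so they do not show that 4 more days would exceed it.
- A reader might conclude that events after Day 21 would go uncollected. Section 10.4 has adverse events reported until study conclusion, Section 9.3 also requires a diary review at the end of study, and Section 11.7.1 collects pregnancy information until 1 day after the last application. Only the scheduled review and test stop at Day 21.

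**Conclusion.** The protocol contradicts itself, in current text, on when treatment ends and when product is returned. The practical size is small: at most 4 days of use beyond the stated 21 (3 if screening is counted as day 1), falling to none with a 7-day baseline. Reaching that maximum assumes a baseline of exactly 3 days, a site that applies the 28-day wording over the explicit 21-day limit, and product not collected at Visit 3. The documents give no distribution of baseline lengths, so the number of subjects who could be affected cannot be estimated. The primary analysis is not affected; recorded exposure, compliance and the timing of the final safety assessments relative to last use could be. This is an inconsistency worth correcting, not evidence that subjects will be over-exposed.

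**What to change.** Reconcile the synopsis (Treatment Duration/Intervention), Table 1-1 and Sections 7.4, 7.7, 9.2.2 and 9.2.3 to one day count and one stated maximum duration of gel use. The SAP already counts from the baseline visit, so a protocol count from the same point would match it. Tie the stop prompt, product return, final adverse event review and final pregnancy test to the same day, whatever the length of baseline. If Section 7.4 is meant to describe the site's return of product to the sponsor, it should say so and drop the subject-level day number. Which limit on use applies is for the sponsor to decide.

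The cost is protocol wording, ethics committee or review board approval of the amendment (Section 14.3.1 requires it in advance), and a memo to sites. No extra visit or procedure is needed.

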### **9.3 Diary Review**

The eDiary should be reviewed at the end of Study, during Day 7,14 and 21 by the investigator, and periodically up to the discretion of investigator (remotely via telephone call or via email communications – this is up to the discretion of the site staff and the subject). Any subject comment captured in the eDiary which is considered an adverse event will be assessed and reported as per the defined procedure in this protocol. Adverse event reporting procedures are summarised in [Adverse Event and Serious Adverse Events](#).

Any additional comments relating to medications/treatments provided in the eDiary will be reviewed by the investigator or medically qualified designee with the subject and investigator entered the eCRF as appropriate.

### **9.4 Study Conclusion**

The Study Conclusion page of the eCRF will be completed for all subjects whether they completed all study procedures or if they were discontinued from the study early. If the subject discontinued early, at any point during the study, the primary reason for withdrawal should be recorded on the Study Conclusion page.

If a subject has any clinically significant, study-related abnormalities or AEs at the end of the study, the Haleon medical monitor (or designated representative) should be notified and, the subject may be asked to remain at the clinical site or be asked to return for a follow-up visit to ensure any issue is resolved or deemed not clinically significant.

### **9.5 Follow-up Visit/Phone Call**

The study site may contact a subject to follow up an AE post-study completion/withdrawal and, in some circumstances, request they return to the site for additional follow-up visits (final safety assessments). If needed, additional examinations may be carried out at such visits.

## **10 STUDY ASSESSMENTS**

Every effort should be made to ensure that protocol-required tests and procedures are completed as described. However, it is anticipated that from time to time there may be circumstances, outside the control of the investigator that may make it unfeasible to complete an assessment. In these cases, the investigator must take all steps necessary to ensure the safety and well-being of the subject. When a protocol-required assessment cannot be performed, the investigator will document the reason for the missed assessment as a protocol deviation and any corrective and preventative actions that he or she has taken to ensure that required processes are adhered to as soon as possible. The Sponsor must be informed of any missed assessments in a timely manner.

## **10.1 Screening Assessments**

Subject enrolment will be determined based on the inclusion/exclusion criteria during screening.

## **10.2 Quality of Life Assessments**

The following quality of life tools will be completed by subjects daily in the subject eDiary from receipt of product to study conclusion.

- WOMAC, NRS and EQ-5D-5L Questionnaire.
- QoL and Sleep/alertness Questionnaires.

## **10.3 Wearable Assessments**

The following wearable assessments will be performed by Actigraph daily and will be correlated with QoL assessments from receipt of product to study conclusion.

- Moderate and Vigorous Physical Activity.
- Physical and sleep based activities.

## **10.4 Safety and Other Assessments**

Subjects will report any adverse events throughout the study from consent to study conclusion.

Subjects will complete an eDiary to record product use each day.

Subjects will complete end of the study questions as outlined to them during consent.

The local investigator will record any relevant medical and surgical history, including allergies or drug sensitivity, and adverse events. The local investigator will also record use of any current medications/treatments, including prescription and non-prescription drugs, dietary supplements, and herbal remedies.

# **11 ADVERSE EVENT AND SERIOUS ADVERSE EVENTS**

The investigator and any qualified designees are responsible for detecting, documenting, and reporting events that meet the definition of an AE or SAE and remain responsible for following up AEs that are serious, considered related to the study product or the study, or that caused the subject to discontinue the study product or study.

## **11.1 Definition of an Adverse Event (AE)**

An AE is any untoward medical occurrence in a clinical study subject, temporally associated with the use of a study product including any washout or lead-in product (or medical device), whether or not considered related to the study product, including any washout or lead-in product (or medical device).

Property of Haleon - Confidential

May not be used, divulged, published or otherwise disclosed without the consent of  
Haleon

Clinical Protocol Template, TMF-187821, v11.0. Parent SOP: **CCI**

**NOTE:** An AE can therefore be any unfavourable and unintended sign (including an abnormal laboratory finding), symptom, or disease (new or exacerbated) temporally associated with the use of a study product including any washout or lead-in product (or medical device).

